## **10.5 Study Population**

The set of randomized patients (see section [10.3](#)) will be used for all study population summaries unless otherwise noted. Summaries will be presented by treatment group and for all patients.

### **10.5.1 Patient Disposition**

Data from patients screened, patients screened but not randomized, patients randomized in the study, patients randomized but not treated, patients in the safety analysis set, patients in the full analysis set, patients who complete the study, and patients who withdraw from the study by reason for discontinuation will be summarized using descriptive statistics.

### **10.5.2 Demographic and Baseline Characteristics**

Patient demographic and baseline characteristics, including medical history, prior medications, and physical examination and 12-lead ECG findings, will be summarized by treatment group and stratification factors and overall. For continuous variables, the descriptive summary statistics will include number (n), mean, standard deviation (SD), standard error (SE), median, minimum, and maximum. For categorical variables, patient counts and percentages will be provided. Categories for missing data will be presented if necessary.

## **10.6 Efficacy Analysis**

Efficacy evaluation will be based on the full analysis set (see section 10.3) that includes all patients who received at least 1 dose of the study drug.

### **10.6.1 Primary Variable**

The primary efficacy variable is the proportion of patients achieving a combined clinical response using the SRI assessed at week 52. An SRI response is defined as a reduction from baseline in the SLEDAI-2K score of at least 4 points, no worsening in PhGA (with worsening defined as an increase in PhGA of more than 0.30 point from baseline), no new BILAG A body system score, and no more than 1 new BILAG B body system score from baseline.

### **10.6.2 Secondary Variables**

Secondary efficacy variables and endpoints are as follows:

- proportion of patients achieving an SRI response at each visit during the treatment period
- proportion of patients achieving a reduction of at least 4 points in the SLEDAI-2K total score at each visit during the treatment period
- proportion of patients achieving a clinical SLEDAI-2K response at each visit during the treatment period, where the clinical response is defined as a reduction of at least 4 points in the SLEDAI-2K clinical score
- proportion of patients achieving a BILAG-2004 response at each visit during the treatment period (no new BILAG A body system score and no more than 1 new BILAG B body system score from baseline)
- proportion of patients achieving a BILAG-2004 clinical response at each visit during the treatment period (an improvement in at least 1 category from a B score to a

- C or D score, with no worsening in any other category)
- proportion of patients showing no worsening on a PhGA scale at each visit during the treatment period
  - proportion of patients achieving a reduction of 5 points in the SLEDAI-2K total score at each visit during the treatment period
  - proportion of patients achieving a reduction of 6 points in the SLEDAI-2K total score at each visit during the treatment period
  - proportion of patients achieving an SRI-5 response at each visit during the treatment period
  - proportion of patients achieving an SRI-6 response at each visit during the treatment period
  - proportion of patients showing an improvement in tender and swollen joint counts using the 28-joint count examination for pain and tenderness at each visit during the treatment period
  - SFI at each visit during the treatment period
    - time to first mild to moderate flare
    - incidence of mild to moderate flare
    - time to severe flare (NOTE: A severe flare leads to early withdrawal)
  - changes in the SDI over time (assessed at screening and weeks 24 and 52 [or final assessment])
  - absolute and relative changes in the SF-36 at weeks 12, 24, 36, and 52 (or final assessment)
  - proportion of patients with changes in steroid dose over time throughout the study.

The exploratory efficacy variables and endpoints for this study are as follows:

- changes in the biomarkers anti-dsDNA Ab, C3, and C4 at each visit during the treatment period
- changes in the following biomarkers at weeks 4, 12, 24, 36, and 52 (or final assessment):
  - ANA
  - anti-U1-70K snRNP Ab
  - anti-Sm Ab
  - CRP
  - IgG, IgM, IgA and IgE
- absolute and relative changes in the FACIT-Fatigue at weeks 12, 24, 36, and 52 (or final assessment)
- in vitro intracellular and secreted cytokine response

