**Statistical Considerations:** The primary efficacy variable is the proportion of patients achieving a combined clinical response using the SRI at week 52. With 100 evaluable patients per group (200 total), this study will have a 90% or greater power to detect a 25% or greater difference or a 20% difference with a 80% power in the proportion of SRI responders between the IPP-201101 group and the placebo group. This projection using the Pearson Chi-square test (2-sided, alpha=0.05) is based on an anticipated placebo effect at week 52 of 40% to 45%. This range covers the placebo effect reported in the literature and in a Phase 2b, multicenter, randomized, double-blind, placebo-controlled dose-ranging study of IPP-201101 (study IP-004). The response rate under active is based on the Phase IIb study performed with the mannitol formulation outside the US. This study showed an absolute 25% response of active over placebo increasing to 40% in the interim analysis. Using a 80% or a 90%power leads to a sample size of 100 evaluable patients per group. The efficacy evaluation will be based on the full analysis set that includes all patients who received at least 1 dose of the study drug.. The statistical method to be used for the SRI is the logistic regression model with treatment and stratification factors as main factors. The SRI is linked to the model factors through the logit function. The likelihood-ratio-based Chi-square statistics will be used for testing the treatment difference between IPP-201101 and placebo in SRI at week 52 at the significance level 0.05. The odds ratio (active/placebo) and associated 95% confidence interval will be determined from the logistic regression model. As sensitivity analyses, the primary analysis will be repeated using another 3 imputation methods to estimate missing SRI at week 52 according to the reason for withdrawal. In the 1st method, patients who withdraw because of lack of efficacy will be classified as treatment failures assessed by SRI at week 52. For patients who withdraw

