## **10.2 Sample Size and Power Considerations**

This study is designed to estimate and assess the significance of the difference between a 200-mcg dose of IPP-201101 and placebo in the proportion of SRI responders at week 52. With 100 evaluable patients per group (200 in total), this study will have 90% or greater power to detect a 25% or greater difference in the proportion of SRI responders between the IPP-201101 group and the placebo group or to detect a 20% difference with an 80% power. This projection using the Pearson

Chi-square test (2-sided,  $\alpha=0.05$ ) is based on an anticipated placebo effect at week 52 of 40% to 45%. This range covers the placebo effect reported in the literature ([Navarra et al 2009](#), [van Vollenhoven et al 2010](#), [Wallace et al 2009](#)) and in a Phase 2b, multicenter, randomized, double-blind, placebo-controlled dose-ranging study of IPP-201101 (study IP-004). The difference between placebo and active which is used in the sample size calculation is 25% based on the results of the Phase IIb study (IP-004) with the same formulation (Zimmer et al. ACR 2012)

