## **10.4 Data Handling Conventions**

All available data will be included for evaluation. For the purpose of efficacy analysis, missing or invalid values will be imputed using data from the previous visit for individual items and scores in the questionnaires and scales. For a derived score involving multiple items, the missing or invalid individual items will be imputed first before calculating the derived scores based on the complete individual item values. These rules apply only to the visits in which the patient is currently in the study and some data or an individual item is missing. If an assessment is not done at a visit, the missing data will not be imputed. The justification for using data from the previous visit is based on medical judgment. For the SF-36 questionnaire, the Half-Scale Missing Data Estimation (Half-Scale MDE) ([Ware et al 2007](#)) method will be used to estimate the missing values for calculating the 8 health domain scales.

Missing or invalid laboratory test results will not be estimated for biomarker analysis or safety analysis.

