#### **10.6.3.2 Secondary Efficacy Analysis**

Secondary efficacy variables will be summarized using the descriptive statistics by treatment group and time point. Safety evaluations will include all patients who received at least 1 dose of study drug. Descriptive statistics will be used to summarize the safety variables.

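### SF-36 is confined to by-arm descriptives of absolute and relative change, so the quality-of-life objective gets no adjusted treatment difference or interval

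*Protocol*

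**What the plan says.** Section 2.2 lists, as a secondary objective, evaluating how the drug affects health-related quality of life measured by SF-36. Section 10.6.2 turns this into the variable "absolute and relative changes in the SF-36 at weeks 12, 24, 36, and 52 (or final assessment" (the bracket closes there). Section 10.6.3.2 states the method: "Secondary efficacy variables will be summarized using the descriptive statistics by treatment group and time point". The synopsis says the same. No model, between-arm difference or interval is named for any secondary variable.

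The primary endpoint is treated differently. Section 10.6.3.1 gives it a logistic regression with the stratification factors, and an odds ratio with a 95% confidence interval.

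SF-36 and FACIT-Fatigue are both collected at visit 2, before the first dose (section 3.11.2 and Table 2). FACIT-Fatigue is in the exploratory list of section 10.6.2, as "absolute and relative changes in the FACIT-Fatigue at weeks 12, 24, 36, and 52 (or final assessment". Section 6.2.4 describes it as a 13-item scale, and Appendix G prints each item with responses from 0 to 4. Section 10.4 refers to eight SF-36 domain scales but does not say whether they are scored 0 to 100 or norm-based.

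**The concern.** An objective about the effect of a drug is a comparison between arms. Separate summaries for each arm do not state that comparison or its uncertainty. The omission is not left open for a later document: section 10.6.3.2 names the method, and that method cannot deliver the objective.

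Two further weaknesses follow. First, a baseline score is available for adjustment and is not used for it. Second, writing relative change into the variable definition puts a poorly behaved quantity beside the sound one, with no statement of which is the main summary. At stake are the precision and interpretability of a patient-reported outcome, and the risk that the choice between absolute and percent change is made after unblinding.

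**Working it through.** **The plan's own figure.** The only power statement concerns the primary SRI endpoint: "With 100 evaluable patients per group (200 in total), this study will have 90% or greater power to detect a 25% or greater difference", or "to detect a 20% difference with an 80% power", and it "is based on an anticipated placebo effect at week 52 of 40% to 45" percent. With the pooled-variance two-proportion formula, two-sided 0.05 and 100 per arm, power is 81.2% (placebo 40%) and 81.6% (placebo 45%) for 20 points, and 94.9% and 95.3% for 25 points. The stated figures reproduce. No figure is stated for SF-36 or FACIT-Fatigue, so none is wrong.

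**Baseline adjustment.** Inputs: 100 per arm (section 10.2); equal SDs at baseline and follow-up (assumed); correlation rho between them (assumed, because the protocol gives none). Per patient, in units of SD²:

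- unadjusted change: 2(1 − rho)
- ANCOVA: 1 − rho²
- ratio: (1 − rho²) / [2(1 − rho)] = (1 + rho)/2

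The 95% CI half-width for the between-arm difference is 1.96 × √(variance) × √(2/100), in SD units. At rho 0.5, unadjusted change gives 1.96 × √1.00 × 0.1414 = 0.277, and ANCOVA gives 1.96 × √0.75 × 0.1414 = 0.240. The last column is 100 × 2/(1 + rho), the size per arm at which unadjusted change matches ANCOVA with 100.

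| rho (assumed) | Variance ratio | Half-width, change | Half-width, ANCOVA | Matching n per arm |
|---|---|---|---|---|
| 0.3 | 0.65 | 0.328 | 0.264 | 154 |
| 0.5 | 0.75 | 0.277 | 0.240 | 133 |
| 0.7 | 0.85 | 0.215 | 0.198 | 118 |
| 0.8 | 0.90 | 0.175 | 0.166 | 111 |

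With fewer than 100 per arm observed at week 52, both half-widths widen but the ratio is unchanged. Any gain from the stratification factors is not counted.

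**Relative change.** A 10-point gain is 10/5 = 200% from a baseline of 5, 100% from 10, 25% from 40, 17% from 60, and undefined from 0. Adding 20 to every score leaves the gain at 10 points but turns 25% (from 40) into 17% (from 60), so the percentage depends on where the scale happens to start. If FACIT-Fatigue is a simple sum of its items, its range is 0 to 13 × 4 = 52, which includes 0. SF-36 domains can be 0 if scored 0 to 100, which is not stated.

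**Illustration, all inputs assumed.** This used 3,000 simulated trials, 100 per arm and rho 0.5, with zero baselines left out of percent change. The proportions significant at 0.05 for absolute change, percent change and ANCOVA were:

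- 72%, 29% and 83% on a 0–52 scale (mean 26, SD 11, effect 4)
- 71%, 20% and 84% on a 0–100 scale (mean 45, SD 25, effect 9)

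Baselines at 0 made up about 1% and 4%. The ordering is informative. The levels are not forecasts for this trial.

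**The case against.** The best defence is that the trial makes one confirmatory test and claims nothing inferential for its secondary variables. Section 10.6.3.2 treats them all alike, absolute change is reported beside relative change, and section 10.11 foresees a complete statistical plan that could add a model. If that plan's descriptives include means and SDs, a reader could work out an unadjusted difference. All of this is fair, and it keeps the point small. It does not remove it: a nominal interval makes no confirmatory claim, and the protocol names a method rather than deferring one.

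The precision figures are also open to challenge, because they are measured against an unadjusted comparison that the plan does not itself make. That stands. They show what adjustment would gain over the obvious alternative, not a loss in a planned test.

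Three stronger readings are tempting, and the documents do not support them.

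- A reader might infer that FACIT-Fatigue is also fixed as descriptives. It is exploratory, and the sentence in 10.6.3.2 covers secondary variables only. Its method is unstated and may properly sit in the statistical plan.
- A reader might infer from the reference to a final assessment that week 52 pools early-withdrawal scores with true week-52 scores, against section 10.4's "If an assessment is not done at a visit, the missing data will not be imputed". The phrase can simply label when data are collected. A score taken at early termination is an assessment that was done, so 10.4 is not contradicted.
- A reader might infer that the most fatigued patients sit near zero on FACIT-Fatigue. The protocol gives no scoring direction. As printed in Appendix G, low responses on most items mean little fatigue.

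**Conclusion.** The point holds for SF-36: the stated method gives the quality-of-life objective no between-arm estimate or interval and makes no adjustment for the visit-2 score. Against an unadjusted change-score comparison, adjustment would cut the variance by 10% to 35% (ratio 0.90 to 0.65). This assumes equal SDs and a correlation of 0.8 down to 0.3, neither of which the protocol supplies.

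The objection to relative change holds for both scales. The undefined-at-zero part is certain to be possible for FACIT-Fatigue only if its total is a sum of the printed items, and for SF-36 only under 0–100 scoring. Dependence on the origin applies under any scoring. This is a cheap improvement to a secondary analysis. It is not an error in a stated figure and does not touch the primary result.

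**What to change.** In section 10.6.3.2, specify for SF-36 an ANCOVA of absolute change at week 52, or a repeated-measures model over weeks 12, 24, 36 and 52 with visit and treatment-by-visit terms. Either should include treatment, visit-2 score and the randomization stratification factors. Report the adjusted week-52 difference with a nominal 95% confidence interval, and state that no confirmatory claim is made.

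In section 10.6.2 and the matching lists, delete relative change for SF-36 and FACIT-Fatigue, or label it supplementary. If it is kept, say how a zero baseline is handled.

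The cost is one paragraph and standard programming before unblinding. It needs no new data and no change to the primary alpha. If the statistical plan already contains such a model, the protocol text only needs to be brought into line.

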### **10.6.3 Planned Method of Analysis**

#### **10.6.3.1 Primary Efficacy Analysis**

The efficacy evaluation will be based on the full analysis set, which will include all patients who receive at least 1 dose of study drug. The statistical method to be used for the SRI is the logistic regression model with treatment and stratification factors as main factors. Patients who withdraw from the study are classified as nonresponders as measured by SRI at week 52 in the primary analysis. The SRI is linked to the model factors through the logit function. The

likelihood-ratio–based Chi-square statistics will be used for testing the treatment difference between IPP-201101 and placebo in SRI at week 52 at the significance level 0.05. The odds ratio (active/placebo) and associated 95% confidence interval will be determined from the logistic regression model.

As sensitivity analyses, the primary analysis will be repeated using another 3 imputation methods to estimate missing SRI at week 52 according to the reason for withdrawal. In the 1st method, patients who withdraw because of lack of efficacy will be classified as treatment failures assessed by SRI at week 52. For patients who withdraw because of other reasons, their missing SRI at week 52 will be estimated using the multiple imputation method (Little and Rubin, 2002). The imputation values will be drawn from the categories formed by treatment group and randomization stratum to which the patient belongs. In the 2nd method, the missing SRI at week 52 will be imputed using the last observation carried forward (LOCF) method. In the 3rd method, patients who withdraw and those completers who used prohibited medication within 8 weeks from week 52 will be classified as nonresponders.

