In order to ensure patient safety, patients who are determined to be treatment failures will be withdrawn from the study. Patients may be treated for treatment failure at the discretion of the investigator. Treatment failure is defined as any of the following:

- occurrence of a severe flare according to the SFI (also results in withdrawal from the study)
- increase in use of background oral corticosteroids beyond 80 mg of prednisone equivalent/week. (NOTE: Treatment of mild/moderate flare is permitted as detailed in section 5.2. The use of steroids for the treatment of a mild or moderate flare or for the treatment of conditions other than SLE will not be permitted beginning at week 44 [visit 14] through week 52 [visit 16].)
- initiation of pulse iv steroid therapy (ie, 250 to 1000 mg iv total daily dose of methylprednisolone)
- increase in the dose of immunosuppressive agents (methotrexate, azathioprine, MMF, leflunomide) above the baseline level
- initiation of new immunosuppressive therapy (cyclophosphamide, methotrexate, azathioprine, cyclosporin, tacrolimus, leflunomide, MMF)

- initiation of therapy with biologics for the treatment of SLEte, azathioprine, cyclosporin, tacrolimus, leflunomide, MMF)

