#### **3.11.4 Procedures After Study Drug Treatment (Visit 16/Week 52)**

Patients who participate in the study in compliance with the protocol for at least 48 weeks of treatment will be considered to have completed the study. Patients who complete all study visits will be eligible for participation in a open-label study to assess the continued effectiveness and safety of IPP-201101 treatment.

If a patient is withdrawn from the study before completion of 48 weeks of study drug treatment, final evaluations will be performed at the last visit. To be evaluable for efficacy, a patient must be treated with at least 1 dose of study drug and must have all components of the SRI (baseline SLEDAI-2K total score, BILAG-2004 body system scores, and PhGA score) available. Patients with ongoing adverse events or clinically significant abnormal laboratory test results (as interpreted by the investigator) will be monitored as described in section 7.1.2 and section 7.2, respectively.

If a patient withdraws from the study during the treatment period, the reason must be determined and recorded on the patient's CRF (see section 4.3). For patients who withdraw consent, every attempt will be made to determine the reason. A blood sample for measurement of the concentration of IPP-201101 will be obtained from all patients who have an adverse event leading to withdrawal from the study and/or all patients who have a serious adverse event.

For patients who complete the study, final evaluations will be performed at visit 16 (week 52). For patients who withdraw prematurely from the study before completion of 48 weeks of study drug treatment, final evaluations will be performed at the last visit. The following procedures will be performed at visit 16 (week 52) or at early termination (before completion of the 48 weeks of study drug treatment), if applicable:

- physical examination
- clinical laboratory tests
- ANA
- anti-dsDNA Ab, C3, and C4
- anti-U1-70K snRNP Ab, anti-Sm Ab, CRP, IgG, IgM, IgE, IgA
- anti-IPP-201101 Ab (NOTE: Any patient with a positive test result for anti-IPP-201101 Ab at the final study visit will be followed with additional immunogenicity testing at 8-week intervals until the level returns to baseline value or the levels are judged by the investigator to be chronic, or the patient is lost to follow-up)
- vital signs measurements (includes systolic and diastolic blood pressures, pulse, and temperature)

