### **5.2 Prior and Concomitant Therapy or Medication**

Any prior or concomitant therapy or medication given to a patient from the start of screening or during study drug administration will be indicated on the CRF. Other medications used for SLE or other disorders will also be captured on the CRF, as detailed below. Dosage and generic name or trade name will be indicated. The sponsor will encode all therapy and medication according to the WHO drug dictionary (WHO Drug).

As described in section 4.1, if the patient is using oral corticosteroids, the weekly cumulative dose must not exceed 80 mg of prednisone equivalent; the weekly dose must be stable over the 4 weeks preceding the 1st dose of study drug. If a patient is taking oral corticosteroids at study entry, the dose may be decreased during the study at the investigator's discretion. The dose of background corticosteroid medication may be increased to treat the patient for minor fluctuations in lupus disease activity (ie, a mild or moderate flare). However, the dose of oral corticosteroid may not exceed 30 mg of prednisone or equivalent per day for more than 2 weeks. If a patient not previously treated with corticosteroids requires initiation of treatment with corticosteroids during the study to treat minor fluctuations in lupus disease activity (ie, a mild or moderate flare), the dose of oral corticosteroid may not exceed 30 mg of prednisone or equivalent per day for more than 2 weeks. If a patient requires a temporary increase in corticosteroid dose or a short course of corticosteroid treatment (ie, 2 weeks) and the medication is unable to be tapered to the baseline dose or be withdrawn, respectively, the patient is to be withdrawn from the study. If a patient requires treatment with corticosteroids for a condition other than SLE, these same restrictions on corticosteroid use, and those detailed in section 4.2, will apply. The use of intra-articular steroids may be allowed after consultation with the medical expert.

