- an inability to reduce corticosteroid dose to the baseline dose or to withdraw therapy if the patient required a temporary increase in corticosteroid dose or a short course of corticosteroid treatment (ie, 2 weeks) and the medication is unable to be tapered to the baseline dose or be withdrawn, respectively
- therapy is initiated with pulse iv steroids
- an increase in the baseline dose of immunosuppressive agents (methotrexate, azathioprine, MMF)
- initiation of new immunosuppressive therapy (cyclophosphamide, methotrexate, azathioprine, cyclosporin, tacrolimus, leflunomide, MMF)
- initiation of therapy with biologics for the treatment of SLE
- any change in the doses of background therapies beginning with week 44 (visit 14) More information is provided in section 3.6 and Appendix B.

Patients will be excluded from participation in the study for any of the following reasons:

- they have been treated with iv pulse steroids within 4 weeks of the 1st dose of study drug
- they have received tacrolimus, cyclosporin A, or IVIG within 3 months of the 1st dose of study drug
- they have received cyclophosphamide or have been treated with biologic agents for SLE, such as fusion proteins, therapeutic proteins, or monoclonal antibodies or antibody fragments, within 6 months of the 1st dose of study drug
- they have received B-cell depleting agents such as rituximab or belimumab within one year of 1st dose of study drug and have not yet normalized the B-cell count
- they have a planned immunization with a live or live attenuated vaccine within 3 months prior to administration of the 1st dose of study drug and for 3 months after the last dose of study drug is administered

More information is provided in section 4.2 and Appendix B.

At each study center visit after the screening visit, the investigator will ask the patient whether any medications (other than study drug), including over-the-counter (OTC) medications, were taken since the previous visit (see Appendix B).

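### Primary nonresponse is tied to withdrawal alone, so a completer with prohibited or escalated SLE medication is scored on the observed SRI although the protocol requires withdrawal

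*Protocol*

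**What the plan says.** **Endpoint.** Section 10.6.1: "An SRI response is defined as a reduction from baseline in the SLEDAI-2K score of at least 4 points", together with conditions on PhGA and on new BILAG A and B scores. Medication plays no part in it.

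**Primary rule.** Section 10.6.3.1: "Patients who withdraw from the study are classified as nonresponders as measured by SRI at week 52 in the primary analysis". Section 10.4 adds that all available data are used.

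**Third sensitivity method.** Same section: "patients who withdraw and those completers who used prohibited medication within 8 weeks from week 52 will be classified as nonresponders".

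**Conduct rules.** Section 3.6: "patients who are determined to be treatment failures will be withdrawn from the study". Its medication criteria are background oral steroids above 80 mg prednisone equivalent per week (outside permitted flare treatment), intravenous pulse steroids, a raised or new immunosuppressant, and a biologic for SLE. Section 5.2 has a largely matching withdrawal list. It adds failure to taper after a temporary steroid course and any background dose change from week 44.

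**Completion.** Section 3.11.4: patients who take part "in compliance with the protocol for at least 48 weeks of treatment will be considered to have completed the study".

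**Detection.** Section 5.2 has the investigator ask about medication at each visit. Table 2 schedules no visit between week 48 and week 52.

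**The concern.** The protocol intends that a patient who needs prohibited or escalated SLE therapy should not count as a responder. It reaches that result indirectly: the medication leads to withdrawal, and withdrawal leads to nonresponse. If the first step is missed, or is recorded as completion, nothing in the primary rule catches the patient. An SRI response reached with a new immunosuppressant, pulse steroids or a biologic would then be credited to the randomized arm. Primary status would depend on a site's disposition entry instead of on the medication record.

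**Working it through.** **1. Primary rule against method 3.** Primary: withdrawn = nonresponder. Method 3: withdrawn = nonresponder, and completer with prohibited medication within 8 weeks of week 52 = nonresponder. The second group is the only difference. If withdrawal caught everyone, the two analyses would be identical, so the protocol foresees completers of this kind and leaves them on the observed SRI in the primary analysis.

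**2. Use first learned of at week 52.** Suppose a patient is compliant through week 48 and starts a prohibited drug in weeks 48 to 52. With no visit in between, the site may first hear of it at the endpoint visit. By 3.11.4 the patient already has 48 weeks of compliant treatment and is a completer. By 5.2 the patient is to be withdrawn. One label gives the observed SRI, the other automatic nonresponse. The protocol does not say which prevails.

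**3. Earlier use.** Method 3 looks back to week 52 − 8 = week 44. A prohibited episode that ended before week 44, in a patient wrongly kept in, is reclassified by none of the four analyses. The other two methods (multiple imputation, LOCF) act only on a missing week-52 SRI. This gap exists only if a mandatory withdrawal was not carried out.

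**4. The plan's power figures.** Inputs from section 10.2: n = 100 per arm, placebo 40% to 45%, differences of 25 and 20 points, Pearson chi-square, two-sided 0.05. With p̄ the mean of the two rates,

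power = Φ{ [ d√n − 1.96√(2p̄(1−p̄)) ] / √(p₀(1−p₀) + p₁(1−p₁)) }.

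For 45% vs 65%: (2 − 1.379)/0.689 = 0.901, so power is 81.6%. The other cases are 40% vs 60%, 81.2%; 40% vs 65%, 94.9%; 45% vs 70%, 95.3%. The stated 80% and at least 90% reproduce.

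**5. Illustration of sensitivity.** The documents give no rate of prohibited use among completers. I assume a net excess of 0 or 2 such responders per 100 in one arm. The figures below come from exact binomial enumeration of the same test without continuity correction, so they differ slightly from step 4.

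| Rates before the excess (placebo / active) | No excess | 2 on placebo | 2 on active |
|---|---|---|---|
| 45% / 65%, power | 82.7% | 74.4% | 89.2% |
| 40% / 60%, power | 82.6% | 74.2% | 89.1% |
| 45% / 70%, power | 95.5% | 91.9% | 97.7% |
| 45% / 45%, chance of significance favoring the drug | 2.7% | 1.4% | 5.1% |

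With 2 in each arm (47% vs 67%) power is 82.9%, essentially unchanged. Only an imbalance matters.

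**6. Why dose alone cannot define failure.** For treatment of a mild or moderate flare, section 5.2 says "the dose of oral corticosteroid may not exceed 30 mg of prednisone or equivalent per day for more than 2 weeks". A permitted course at that dose is 30 × 7 = 210 mg/week, above the 80 mg/week background limit. A rule based on dose alone would fail permitted courses.

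**The case against.** The strongest reply is that the conduct rules already do the work. Withdrawal is mandatory for these medications and every withdrawal is a nonresponse, so what remains is site nonadherence, and method 3 covers the weeks 44 to 52 in which background therapy is frozen. Most of this stands: the affected group is limited to patients who should have been withdrawn but were not recorded so. It does not settle the week-52 case, where two protocol sections point in opposite directions.

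Second, a late start can do little. SLEDAI-2K scores manifestations of the last 4 weeks and BILAG-2004 also refers to the last 4 weeks, so a drug begun after week 48 cannot erase most activity within that window. Rash, alopecia and mucosal ulcers, which the glossary scores as ongoing, are the exception. This also stands, and it limits the benefit that such a patient could show.

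Third, detection does not rest on questioning alone: the flare form records prednisone increases and several new immunosuppressants. True, but at week 52 it is completed at the same visit and does not decide the classification.

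Fourth, an analysis plan, not shown, could add a rule. The protocol has not left the matter open, however. It fixes the primary rule and assigns prohibited medication in completers to a sensitivity analysis.

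A reader might also infer that everyone concerned is a treatment failure on rescue therapy. The documents do not support that. Section 3.6 lists neither failure to taper nor a background dose change from week 44. Both stand only in 5.2, and the latter includes dose reductions, which are not rescue.

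**Conclusion.** The point holds as a gap in the primary rule. A completer whose medication required withdrawal under 3.6 or 5.2 is scored on the observed SRI, and for use discovered at week 52 the protocol classifies the same patient in two ways. It is worth correcting because it concerns the primary endpoint and the correction is cheap.

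Its size may be nil. If every mandatory withdrawal is carried out and recorded, including for changes first learned of at week 52, the effect is zero. Otherwise the protocol gives no basis for size or direction. The excess of 2 per 100 is an assumption; it shows only that the 20-point scenario, powered near 80%, has little room for imbalance. A reader might infer from the table that the primary analysis favors the drug or inflates the false-positive rate. The documents do not support that: the same assumption on the placebo side gives the opposite result, and equal numbers in both arms leave power essentially unchanged.

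**What to change.** Amend section 10.6.3.1 so that the primary nonresponders are:

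- patients who withdraw; and
- patients whose recorded medication up to week 52 meets a 3.6 treatment-failure medication criterion or a 5.2 mandatory medication-withdrawal criterion, whether or not they were withdrawn.

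State the exemptions: steroid courses that 5.2 permits before week 44, for mild or moderate flare or for conditions other than SLE, and medication holidays or tapers agreed with the medical monitor before week 44. Settle unclear cases by blinded review before database lock. Keep the withdrawal-only rule as a sensitivity analysis in place of method 3. Do not describe late dose reductions as rescue; they count only because 5.2 already requires withdrawal for them.

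With these exemptions the rule carries the protocol's existing withdrawal criteria into the analysis and adds no new one. The cost is amendment wording, one derivation from concomitant medication data that 5.2 already puts on the CRF, and a small blinded review. Response rates may fall slightly in both arms.
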